1.1.1 Change in primary endpoint

The data from the Humanigen -sponsored LIVE-AIR trial also gave an opportunity to understand the performance of primary endpoint chosen for this trial. The ordinal score on Day 8 was previously chosen to reflect early improvement in disease. This endpoint had tested well using ACTT-1 data, a study conducted early in the pandemic. However, using the LIVE-AIR data, median ordinal score on Day 8 was 2 for both the lenzilumab and placebo arms in the subgroup, $p = 0.156$ (note: OS2 in the scale used in this trial was called OS7 in the LIVE-AIR trial). Approximately 75% of each arm was discharged by Day 8, which are very different trajectories for recovery and hospital discharge when compared to data obtained early in the pandemic (ACTT-1 data).

Survival without ventilation (Cox proportional hazard model with proportions from using a time to event approach) was the primary endpoint in the LIVE-AIR study. This endpoint also tested well in ACTT-1 and ACTT-2 data and was chosen as the endpoint used in the ACTT-4 trial. Given the overall improvement in care in most patients before Day 8, coupled with the performance of survival without ventilation in several trials, changing the primary endpoint to survival without ventilation is justified. Because the timing of ventilation and death within the 29-day timeframe is less clinically important than its occurrence, the new endpoint is the binary version; that is, incidence of mechanical ventilation or death by Day 29.

The subgroup ordinal scale 5 or 6 at baseline with a CRP<150 mg/L and age<85 years was a post hoc analysis in the LIVE-AIR trial. 78% of patients with a baseline CRP assessment in LIVE-AIR had a CRP level of <150 mg/L. As noted above, this cutoff increased the ability to detect a difference in treatment arms and demonstrated a group of patients that may derive the greatest benefit. It is recognized that the treatment effect in the post hoc subgroup may be overly optimistic. However, the cutoff of CRP < 150 mg/L has been reported as a cutoff for subgroups that may benefit more from certain other COVID therapeutics (7), providing some albeit limited assurance that analysis in this subgroup may improve the power for detecting differences in efficacy between lenzilumab and placebo.

Study Design

See the Master protocol document for a description of the study design.

Study Objectives

See [Table 4](#) in [Section 3](#).

Study Population

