## Appendix 6 BET-B

Endpoint	Analysis	Imputation/Censoring Method
mg/L.	Sensitivity	
 
Use the complete data for ordinal score to define survival without respiratory failure.
 
Subjects whose last assessment in the study is before Day 29 and were discharged to a location other than LTAC, hospice care or other hospital, or progressed to mechanical ventilation or death after Day 29 will be considered non-events and censored at Day 29.
 
Subjects whose last assessment in the study is before Day 29 and before progression to mechanical ventilation or death and without being discharged to a location other than LTAC, hospice care or other hospital at their last assessment will be considered non-events and censored at the date of their last observed assessment.
 
Subjects who complete follow-up without mechanical ventilation or death will be censored at the expected study Day 29.
 

Time to Sustained Recovery up to Day 60 in subjects who are < 85 years old, have baseline clinical status of 5 or 6, and baseline CRP < 150 mg/L.	Primary and subgroup	
 
Use the complete data for ordinal score to derive sustained recovery.
 
Subjects whose last assessment in the study is prior to Day 60 prior to recovery will be considered not recovered and censored at the date of last follow-up.
 
Death prior to recovery will be considered not recovered and censored at expected study Day 60.
 

	Sensitivity	
 
Use the complete data for ordinal score to derive sustained recovery.
 
Subjects whose last assessment in the study is prior to Day 60 after discharge from the hospital to a location other than LTAC, hospice care or other hospital will be treated as recovered by Day 60. Their time to recovery will be the day the time of their first observed/imputed recovery score (i.e; 1, 2, 3) or the day of discharge, whichever comes first.
 
Subjects whose last assessment in the study is prior to Day 60 without being discharged from the hospital to a location other than LTAC, Hospice care or other hospital at their last assessment will be considered not recovered and censored at the date of last follow-up.
 
Death prior to recovery will be considered not recovered and censored at expected study Day 60.
 

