### 8.2.1. Time to Mechanical Ventilation or Death Up to and Including Day 29 for Primary Endpoint Subgroup and All Subjects in ITT Population

The time to mechanical ventilation or death up to and including Day 29 will be defined as the elapsed time (in days) from Study Day 1 to date of invasive mechanical ventilation/ECMO or death. For the primary analysis of this endpoint, all subjects lost to follow-up or terminated early prior to death or progression to invasive mechanical ventilation will be considered non-events and censored at the date of their last observed assessment. As sensitivity analysis of this endpoint, any subjects that are lost to follow-up or terminated early prior to death or progression to mechanical ventilation and were discharged to a location other than LTAC, hospice care or other hospital, or progress to invasive mechanical ventilation/ECMO or death after Day 29 will be considered non-events and censored at Day 29 while subjects that are lost to follow-up or terminated early before Day 29 and before progression to invasive mechanical ventilation/ECMO or death and were either still hospitalized or discharged to LTAC, hospice care or other hospital at their last assessment will be considered non-events and censored at the date of their last observed assessment. If it is learned that a subject who terminated early had subsequently received ventilation or died prior to Day 29, then the subject will be classified as having the event. Subjects who complete follow-up without an event will be censored at the date of their expected Study Day 29 visit. Events that occur after Day 29 will be censored at the expected Study Day 29 date.

Table 7 will present median time to event along with corresponding 95% confidence intervals for each Lenzilumab + RDV long with the hazard ratio estimate and p-value from a Cox proportional hazards model for subjects in the primary subgroup. Restricted mean survival time estimates (RMST) which do not rely on the proportionality assumption will be provided for each treatment group and actual baseline ordinal score stratum as well as the difference in restricted mean recovery time between treatment groups within each of the

baseline ordinal score strata for the primary subgroup ([Table 9](#)). For both the Cox proportional hazards model and the RMST method, tied event times will be handled using the Efron method.

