### **8.2.2. Time to Sustained Recovery Up to and Including Day 60 for Primary Endpoint Subgroup in the ITT Population**

Recovery will be defined as having a value of 1, 2, or 3 on the clinical status 8-point ordinal scale or discharge from the hospital to a location other than LTAC, hospice care, or other hospital. The time to sustained recovery will be defined as the elapsed time (in days) from Study Day 1 to the day prior to the earliest recorded day at which a subject reaches recovery and doesn't worsen (ordinal score  $> 3$ ) up to and including Study Day 60. This analysis will be conducted on the ITT population for those subjects who at baseline have a clinical status score of 5 or 6, CRP $<150$  mg/L, and age $\leq 85$  years. For the primary analysis of this endpoint, all subjects lost to follow-up or terminated early prior to recovery will be considered not recovered and censored at the date of their last observed assessment, regardless of their discharge status. As sensitivity analysis of this endpoint, any subjects that are lost to follow-up or terminated early prior to recovery and were discharged to a location other than LTAC, hospice care or other hospital will be considered recovered by study Day 60 with a time to recovery of time of discharge or time of first score of 1, 2, or 3, whichever comes first, while subjects that are lost to follow-up or terminated early before Day 60 before recovery, were still hospitalized or were discharged to LTAC, hospice care or other hospital at their last assessment will be considered not recovered and censored at the date of their last observed assessment.

Refer to [Table 1](#) for a list of covariates and subgroup analyses for this endpoint. Refer to [Table 2](#) for imputation methods to be applied to this endpoint.

The primary analysis time to sustained recovery up to and including Study Day 60 conducts a score test to compare treatment to control up to and including Study Day 60. The treatment median survival time, confidence intervals and p-value from the score test will be presented ([Table 10](#)). Restricted mean recovery time estimates will be provided for each treatment group and actual baseline ordinal score stratum as well as the difference in restricted mean recovery time between treatment groups within each of the baseline ordinal score strata ([Table 12](#)).

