Kaplan-Meier curves for each Lenzilumab + RDV will be presented and supplemented with the hazard ratio estimate, p-value, and the number of subjects at risk in each Lenzilumab + RDV Study Day (not necessarily actual Study Days 1, 3, 5, 8, 11, 15, 22, 29, and 60) ([Figure 3](#)).

Each subgroup from [Table 1](#) will be considered separately, and the tabular and graphical summaries described above will be replicated for each subgroup ([Table 10](#)). A forest plot will be generated to display 95% CIs for hazard ratios from each of the subgroup analyses ([Figure 7](#)).

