## Programming

Within an actual baseline ordinal score stratum:

```
proc lifetest data=enrevent plots=(rmst) method=breslow rmst(cl);
by stratum;
time evntday * Censor(1);
strata trtcode /diff=all;
ods output rmst=rmst;
run;
```

**Table 10: Time to Sustained Recovery through Day 60 — ITT Population with Baseline Ordinal Score of 5 or 6, CRP<150 mg/L, and age<85 years**

Analysis/Subgroup	Treatment	Number of Recovered Subjects		Median Time Until Recovery		Hazard Ratio		P-value e			
		n	%	Estimate	95% CI	Estimate	95% CI				
Initial Model a	Lenzilumab + RDV (N=X)	x	x.x	x.x	x.x, x.x	x.x	x.x, x.x	0.xxx			
	Placebo + RDV (N=X)	x	x.x	x.x	x.x, x.x						
Sensitivity Analyses											
Sensitivity Analysis 1: Imputation for good discharges b	Lenzilumab + RDV (N=X)	x	x.x	x.x	x.x, x.x	x.x	x.x,x.x	0.xxx			
	Placebo + RDV (N=X)	x	x.x	x.x	x.x, x.x						
Supplemental Analysis 1: Impact of age and duration of symptoms c	Lenzilumab + RDV (N=X)	x	x.x	x.x	x.x, x.x	x.x	x.x, x.x	0.xxx			
	Placebo + RDV (N=X)	x	x.x	x.x	x.x, x.x						
Subgroup Analysesd											
Baseline Ordinal Score											
5	Lenzilumab + RDV (N=X)	x	x.x	x.x	x.x, x.x	x.x	x.x, x.x	0.xxx			
	Placebo + RDV (N=X)	x	x.x	x.x	x.x, x.x						
6	Lenzilumab + RDV (N=X)	x	x.x	x.x	x.x,x.x	x.x	x.x, x.x	0.xxx			
	Placebo + RDV (N=X)	x	x.x	x.x	x.x,x.x						
7	Lenzilumab + RDV (N=X)	x	x.x	x.x	x.x,x.x	x.x	x.x, x.x	0.xxx			
	Placebo + RDV (N=X)	x	x.x	x.x	x.x,x.x						
	P-value for interaction e							0.xxx			
Baseline Steroid Use											
Yes	Lenzilumab + RDV (N=X)	x	x.x	x.x	x.x,x.x	x.x	x.x,x.x	0.xxx			
	Placebo + RDV (N=X)	x	x.x	x.x	x.x,x.x						
No	Lenzilumab + RDV (N=X)	x	x.x	x.x	x.x,x.x	x.x	x.x,x.x	0.xxx			
	Placebo + RDV (N=X)	x	x.x	x.x	x.x,x.x						
	P-value for interaction e							0.xxx			
Baseline Use of Emerging Covid-19 Treatments											
Yes	Lenzilumab + RDV (N=X)	x	x.x	x.x	x.x,x.x	x.x	x.x,x.x				
	Placebo + RDV (N=X)	x	x.x	x.x	x.x,x.x						

Analysis/Subgroup	Treatment	Number of Recovered Subjects		Median Time Until Recovery		Hazard Ratio		P-value e
		n	%	Estimate	95% CI	Estimate	95% CI	
No	Lenzilumab + RDV (N=X)	x	x.x	x.x	x.x,x.x	x.x	x.x,x.x	0.xxx
	Placebo + RDV (N=X)	x	x.x	x.x	x.x,x.x			
	P-value for interaction e							0.xxx
Duration of Symptoms Prior to Enrollment Group 1								
≤ Median	Lenzilumab + RDV (N=X)	x	x.x	x.x	x.x,x.x	x.x	x.x,x.x	0.xxx

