**Table 11: Time to Sustained Recovery through Day 60 — ITT Population**

*[Implementation note: Add subgroup analysis for baseline CRP < 150 mg/L vs baseline CRP  $\geq$  150 mg/L. Add footnote that analysis for this subgroup analysis will only include subjects in the ITT population with baseline ordinal score of 5 or 6 and age < 85 years.]*

**Table 12: Time to Sustained Recovery through Day 60 by Treatment Group, Actual Baseline Ordinal Score, and Analysis Population: Restricted Mean Survival Time Analysis**

Analysis Population	Treatment Group	Actual Baseline Ordinal Score	n	Tau a	Restricted Mean Recovery Time (Days)		Difference	
					Estimate	95% CI	Estimate	95% CI
ITT with BOS 5 or 6, CRP<150 mg/L, and age<85 years	Lenzilumab + RDV (N=X)	5	x	x	x.x	x.x, x.x	x.xx	x.xx, x.xx
	Placebo + RDV (N=X)		x	x	x.x	x.x, x.x		
	Lenzilumab + RDV (N=X)	6	x	x	x.x	x.x, x.x	x.xx	x.xx, x.xx
	Placebo + RDV (N=X)		x	x	x.x	x.x, x.x		
	Lenzilumab + RDV (N=X)	Any BOS b	x	x	x.x	x.x, x.x	x.xx	x.xx, x.xx
	Placebo + RDV (N=X)		x	x	x.x	x.x, x.x		
ITT	Lenzilumab + RDV (N=X)	5	x	x	x.x	x.x, x.x	x.xx	x.xx, x.xx
	Placebo + RDV (N=X)		x	x	x.x	x.x, x.x		
	Lenzilumab + RDV (N=X)	6	x	x	x.x	x.x, x.x	x.xx	x.xx, x.xx
	Placebo + RDV (N=X)		x	x	x.x	x.x, x.x		
	Lenzilumab + RDV (N=X)	7	x	x	x.x	x.x, x.x	x.xx	x.xx, x.xx
	Placebo + RDV (N=X)		x	x	x.x	x.x, x.x		
	Lenzilumab + RDV (N=X)	Any BOS b	x	x	x.x	x.x, x.x	x.xx	x.xx, x.xx
	Placebo + RDV (N=X)		x	x	x.x	x.x, x.x		

N= Number of subjects in the specified treatment group, actual baseline ordinal score, and analysis population.

n = Number of recovered subjects.

Difference is the difference in the restricted mean recovery time between active treatment to placebo.

a Tau is the truncation time point for the Restricted Mean Survival Time analysis and is equal to the minimum of the largest observed times in each group.

b There were X additional subjects with an Actual Baseline Ordinal Score of 4 that are included in the 'Any BOS' summaries.

Programming notes:

Within an actual baseline ordinal score stratum:

```
proc lifetest data=enrevent plots=(rmst) method=breslow rmst(cl);
by stratum;
time evntday * Censor(1);
strata trtcode /diff=all;
ods output rmst=rmst;
run;
```

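### The RMST programs request the Breslow survival curve, against the SAP text and the Kaplan-Meier figures; mean recovery times in Table 12 would come out about 0.6 to 1.5 days too long

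*SAP*

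**What the plan says.** Three places in the SAP bear on which survival curve the RMST comes from.

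- **Text.** Section 8.2.1, on time to ventilation or death, states: "For both the Cox proportional hazards model and the RMST method, tied event times will be handled using the Efron method". Section 8.2.2 plans restricted mean recovery times but gives no tie rule of its own.
- **Programs.** The note under Table 9 reads "proc lifetest data=enrevent plots=(rmst) method=breslow rmst(cl" and so on. The note under Table 12 (sustained recovery) repeats the same line.
- **Figures.** Section 8.2.2 says: "Kaplan-Meier curves for each Lenzilumab + RDV will be presented and supplemented with the hazard ratio estimate", and Figures 1 to 4 are titled as Kaplan-Meier plots.

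Three further statements decide how much the choice of curve matters for recovery. Time is counted in whole days (8.2.2): "The time to sustained recovery will be defined as the elapsed time (in days) from Study Day 1". Deaths stay in the risk set to the end (Table 2): "Death prior to recovery will be considered not recovered and censored at expected study Day 60". The truncation point is set by the data, as the smaller of the two arms' values (footnote to Table 12, cut before its last words): "Tau is the truncation time point for the Restricted Mean Survival Time analysis and is equal to the minimum of the largest observed times in".

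**The concern.** The text names one tie convention, the code another, and the figures show a third curve. A programmer cannot follow both the text and the code. The Breslow curve is never below Kaplan-Meier, and the gap widens when many events fall on the same day. Recovery is that case: whole-day times, and most subjects recovering early. Once a gap has opened, it is carried along the plateau to Day 60 formed by subjects who never recover.

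At stake are the arm-level restricted means in Table 12, which the shell prints to 0.1 day by baseline ordinal score. They would be too long, and a reader could not recover them from the Kaplan-Meier curves. RMST is in the plan because it does not need proportional hazards, so its values should be reproducible from the curve shown.

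**Working it through.** **Plan's own figure.** The documents state no RMST value to reproduce. The 200 per arm used below (half of the 400 in the subgroup) does reproduce the stated power at odds ratio 2.5 and two-sided alpha 0.049: 79.7% against 80% at a 16% control rate, and 88.7% against 89% at 21%.

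**Assumption throughout.** RMST is the area under the curve named in the method option, from 0 to tau. For recovery, tau is taken as 59 elapsed days (Day 1 to Day 60).

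**Step 1: three curves.** With n at risk and d events on a day:

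- Kaplan-Meier: product of (1 − d/n)
- Breslow: exp(−Σ d/n)
- Tie-corrected, the curve-level counterpart of Efron: exp(−Σ over days of Σ 1/(n − j), j = 0 to d − 1)

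Take one day with 200 at risk and 32 recoveries. Kaplan-Meier gives 168/200 = 0.8400. Breslow gives exp(−0.16) = 0.8521. The tie-corrected sum is about ln(200.5/168.5) = 0.1739, giving 0.8404. The stated Efron rule therefore lies close to Kaplan-Meier; the coded rule does not.

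**Step 2: the first week.** Protocol 1.1.1 reports for LIVE-AIR: "Approximately 75% of each arm was discharged by Day 8". Treat discharge as recovery at a constant daily hazard h:

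- h = 1 − 0.25^(1/8) = 0.1591
- Kaplan-Meier at Day 8: (1 − 0.1591)^8 = 0.250
- Breslow at Day 8: exp(−8 × 0.1591) = exp(−1.273) = 0.280

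The ratio is 0.280/0.250 = 1.12, and it cannot fall later because exp(−x) ≥ 1 − x. The area between the curves over these eight days is 0.18 day.

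**Step 3: the plateau.** Assume 90% recovered by Day 60, so Kaplan-Meier never drops below 0.10. Over the remaining 59 − 8 = 51 days the extra area is at least 0.12 × 0.10 × 51 = 0.61 day. The total is then at least 0.18 + 0.61 = 0.79 day per arm, before counting the decline from 0.25 to 0.10.

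**Step 4: simulated recovery.** Inputs: lognormal times (log-scale SD 0.7) rounded up to whole days, non-recovered held to Day 60, 300 trials per setting.

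| Per arm | Median, share recovering | Kaplan-Meier | Breslow | Excess |
|---|---|---|---|---|
| 200 | 6 days, 90% | 13.2 | 14.1 | +0.95 |
| 200 | 11 days, 85% | 21.1 | 21.7 | +0.58 |
| 40 | 5 days, 93% | 10.5 | 12.0 | +1.51 |

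A wider grid (exponential or lognormal times, 85 to 98% recovered) agrees:

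- 75% recovered by Day 8: +0.8 to +1.7 days at 100 to 200 per arm, and up to +1.9 at 50.
- 10-day median (the ACTT-1 remdesivir figure in Protocol 2.2.2): +0.6 to +0.9 days, and up to +1.1 at 50.

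The values above 1.5 come from fast early recovery with a high plateau or small arms. The tie-corrected curve exceeded Kaplan-Meier by about 0.1 day at 200 per arm and 0.4 to 0.5 at 50.

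**Step 5: between-arm difference.** With 200 per arm, medians of 6 against 7 days and 90% against 85% recovering, the difference is −3.70 days by Kaplan-Meier and −3.59 by Breslow. The shift is 0.11 day against a sampling SD of about 1.7. In the other settings run it was 0.09 to 0.18 day, the larger values at 40 per arm.

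**Step 6: Table 9.** Put a 21% event rate entirely in the first eight days: h = 1 − 0.79^(1/8) = 0.0290. Kaplan-Meier ends at 0.7900 and Breslow at exp(−0.2323) = 0.7927. The gap of 0.0027 over 29 − 8 = 21 days is 0.06 day. Across event rates of 7 to 21% the total excess was 0.004 to 0.09 day.

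**The case against.** The strongest reply is that nothing of consequence turns on this, and much of it stands.

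- The Efron sentence sits in 8.2.1, on ventilation or death, where the choice of curve is worth less than 0.1 day. The recovery section states no tie rule. Section 8.2.4 does send the all-subjects recovery analysis back to 8.2.1, but that looks like a cross-reference slip. So the explicit text-against-code conflict and the sizeable effect belong to different endpoints. For recovery, the mismatch is between the code and the Kaplan-Meier figures.
- RMST is not tested. The first key secondary takes its p-value from a Cox model, recovery uses a score test, the hierarchy in 6.8 does not mention RMST, and Tables 9 and 12 have no p-value column.
- The size rests on assumed recovery curves and on software behaviour that the documents do not describe.

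A reader might infer that the treatment effect on recovery is materially shrunk, or that a key secondary conclusion is at risk. The documents and the arithmetic do not support either: both arms shift the same way by nearly the same amount, and no decision uses these tables. A reader might also want tau fixed at 29 or 60. The SAP defines tau explicitly, and changing it is a separate preference that this inconsistency does not call for.

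The reply does not make the text, the programs and the figures agree, and it does not make the Table 12 arm means right.

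**Conclusion.** Wrong as written, and minor. The mismatch between text, programs and figures is certain from the SAP alone. Its numerical effect is conditional on the procedure integrating the requested curve and on recovery patterns like those assumed. On that footing each arm's restricted mean recovery time is overstated by about 0.6 to 1.5 days, somewhat more in the extreme corners of the grid and in small ordinal-score strata. That is roughly six to fifteen times the 0.1-day precision of the Table 12 shell. The between-arm difference changes by about 0.1 day, Table 9 is practically unaffected, and the primary and key secondary tests do not change.

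**What to change.** In the program notes under Tables 9 and 12, request the product-limit (Kaplan-Meier) estimator in place of Breslow. In 8.2.1, limit the Efron sentence to the Cox model. State once, in 8.2.1 and 8.2.2, that RMST is the area under the Kaplan-Meier curve up to the tau already defined; leave that definition unchanged. The cost is one keyword in each of two programs and a few words of SAP text. No data collection, sample size or testing procedure changes.

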**Table 11: Time to Sustained Recovery through Day 60 — ITT Population**

*[Implementation note: Add subgroup analysis for baseline CRP < 150 mg/L vs baseline CRP  $\geq$  150 mg/L. Add footnote that analysis for this subgroup analysis will only include subjects in the ITT population with baseline ordinal score of 5 or 6 and age < 85 years.]*

**Table 12: Time to Sustained Recovery through Day 60 by Treatment Group, Actual Baseline Ordinal Score, and Analysis Population: Restricted Mean Survival Time Analysis**

Analysis Population	Treatment Group	Actual Baseline Ordinal Score	n	Tau a	Restricted Mean Recovery Time (Days)		Difference	
					Estimate	95% CI	Estimate	95% CI
ITT with BOS 5 or 6, CRP<150 mg/L, and age<85 years	Lenzilumab + RDV (N=X)	5	x	x	x.x	x.x, x.x	x.xx	x.xx, x.xx
	Placebo + RDV (N=X)		x	x	x.x	x.x, x.x		
	Lenzilumab + RDV (N=X)	6	x	x	x.x	x.x, x.x	x.xx	x.xx, x.xx
	Placebo + RDV (N=X)		x	x	x.x	x.x, x.x		
	Lenzilumab + RDV (N=X)	Any BOS b	x	x	x.x	x.x, x.x	x.xx	x.xx, x.xx
	Placebo + RDV (N=X)		x	x	x.x	x.x, x.x		
ITT	Lenzilumab + RDV (N=X)	5	x	x	x.x	x.x, x.x	x.xx	x.xx, x.xx
	Placebo + RDV (N=X)		x	x	x.x	x.x, x.x		
	Lenzilumab + RDV (N=X)	6	x	x	x.x	x.x, x.x	x.xx	x.xx, x.xx
	Placebo + RDV (N=X)		x	x	x.x	x.x, x.x		
	Lenzilumab + RDV (N=X)	7	x	x	x.x	x.x, x.x	x.xx	x.xx, x.xx
	Placebo + RDV (N=X)		x	x	x.x	x.x, x.x		
	Lenzilumab + RDV (N=X)	Any BOS b	x	x	x.x	x.x, x.x	x.xx	x.xx, x.xx
	Placebo + RDV (N=X)		x	x	x.x	x.x, x.x		

N= Number of subjects in the specified treatment group, actual baseline ordinal score, and analysis population.

n = Number of recovered subjects.

Difference is the difference in the restricted mean recovery time between active treatment to placebo.

a Tau is the truncation time point for the Restricted Mean Survival Time analysis and is equal to the minimum of the largest observed times in each group.

b There were X additional subjects with an Actual Baseline Ordinal Score of 4 that are included in the 'Any BOS' summaries.

Programming notes:

Within an actual baseline ordinal score stratum:

```
proc lifetest data=enrevent plots=(rmst) method=breslow rmst(cl);
by stratum;
time evntday * Censor(1);
strata trtcode /diff=all;
ods output rmst=rmst;
run;
```

